8.2. Statistical Analyses

8.2.1. Primary Analysis

The primary analysis will be based on the Safety Analysis Set. The analysis objective is to summarize the adverse event incidence and will implement Pfizer standard summaries for adverse events. The occurrence of DLTs observed in the dosing cohorts is used to estimate the MTD as described in the Study Design section. Adverse Events constituting DLTs will be listed per dose level. Because the intent is to find a desirable dose that meets the tolerability criteria based on DLT rate while demonstrating clinical activity based on response rate, descriptive statistics (n, frequency, and percentage) will be reported.

Corresponding listings of data will be generated. Adverse events and cytokine release syndrome will be summarized by dose cohorts and in aggregate.

8.2.2. Efficacy Analyses

No formal hypothesis testing will be performed on analysis of efficacy endpoints.

Efficacy analysis will be summarized by dose cohorts. Analysis of progression free survival and time to progression are defined as time from the date of first dose. Summaries of the n and % of subjects with PFS, and TTR and data listing by tumor type and dose will be generated. If applicable, the PFS may also be summarized using the Kaplan-Meier method at all or some of the following timepoints:

- OS at 6, 9, 12, 18, 24 months timepoints
- PFS, DOR, DoSD and DoCR at 3, 6, 9, 12, 18 months timepoints
- Reverse KM Follow-up probability is 3, 6, 9 months timepoints

The 95% confidence intervals will be generated. Confidence intervals for medians and quartiles will be based on the Brookmeyer-Crowley method. Confidence intervals for the estimated probability of an event at a particular time point will be generated using the Greenwood formula. Duration of response will be summarized with number of responders, number and percentage of event/censorship, mean, standard deviation, minimum, maximum and median of duration in unit of months. ORR and CBR will be summarized by number of subjects meeting respective criteria, percentage. The 95% confidence intervals will be generated for PFS, TTR, ORR, and CBR. Definitions of PFS, TTR, DoR, ORR, and CBR are outlined below.

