9.4. Efficacy Analysis

In this First in Patient study, anti-myeloma activity is a secondary objective in Part 1 dose escalation. Objective response rate (ORR) and duration of response (DOR) are primary objectives in Part 2 dose expansion. Other efficacy endpoints are secondary objectives in Part 2. The analysis population is defined in [Section 9.1](#) Analysis Sets.

Imaging studies, relevant laboratory assessments, and bone marrow pathology may be collected to support independent central review for efficacy endpoints.

PF-06863135

C1071001

Final Protocol Amendment 9, 28 March 2023

Disease response will be presented in the form of patient data listings that include, but are not limited to starting dose, disease response at each visit, and best overall response. In addition, progression date, death date, date of first response and last disease assessment date, and date of last contact will be listed.

Best overall response (BOR) will be assessed based on reported overall responses at different evaluation time points using IMWG response criteria (see [Appendix 2](#)).^{4,5}

- **Complete Response** will encompass confirmed stringent Complete Response (sCR) and Complete Response (CR).
- **Overall Response (OR)** will encompass confirmed sCR, CR, VGPR (very good partial response) and partial response (PR).
- **Clinical Benefit (CB)** will encompass confirmed sCR, CR, VGPR, PR and MR.

Progression -free survival (PFS) is the time from start date of study treatment to date of first documentation of progression, or death due to any cause. Progression is defined as the appearance of local, regional or distant disease of the same type after complete response or progression of pre-existing lesions. It does not include second primary malignancies of unrelated types.

Overall survival (OS) is the time from start date of study treatment to date of death due to any cause.

Duration of Complete Remission is defined for patients with confirmed complete response (sCR, CR) as the time from the first documentation of complete response to the first documentation of objective tumor progression or to death due to any cause, whichever occurs first.

Duration of Response (DOR) is defined for patients with confirmed objective response (as defined above in overall response) as the time from the first documentation of objective tumor response to the first documentation of objective tumor progression or to death due to any cause, whichever occurs first.

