8.1.4. Analyses for Time-to-event Data

The median, percentiles, and probabilities at particular points in time are estimated using the method of Kaplan and Meier. Kaplan-Meier estimates (product-limit estimates) will be presented and displayed graphically where appropriate, together with a summary of associated statistics including the median PFS time with 2-sided 95% CIs. The CIs for the median will be calculated according to Brookmeyer and Crowley, 1982.⁶

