8.2.2.6. Duration of Response (DoR)

DoR is defined, for participants with an objective response per IMWG criteria, as the time from the first documentation of objective response that is subsequently confirmed, until PD per IMWG criteria, or death due to any cause, whichever occurs first. It will be calculated as follows:

$$\text{DoR (months)} = [\text{date of event or censoring} - \text{first date of objective response} + 1] / 30.4375$$

The censoring rules for DoR are as described for PFS in Section 8.2.2.1, except that participants will not be censored for inadequate baseline assessment or for no adequate post-baseline assessment, as only participants with an objective response are included in the analysis of DoR.

If at least 3 participants achieve an objective response and subsequently have an event, DoR will be estimated using the same Kaplan-Meier method as described for PFS in Section 8.2.2.1 and displayed graphically where appropriate. Otherwise, only listings will be provided.

The DoR rate at 3, 6, 9, 12 and 18 months (and in subsequent 6-month increments while there are participants still at risk) will be estimated with corresponding two-sided 95% CIs.

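### SAP 8.2.2 asks for a mean and SD of duration of response, a censored Part 2 primary endpoint, without handling censoring, and its unconditional summary conflicts with the listings-only rule in 8.2.2.6

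*SAP*

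**What the plan says.** Protocol 9.4 sets the status of the endpoint: "Objective response rate (ORR) and duration of response (DOR) are primary objectives in Part 2 dose expansion". SAP 2.2.2 agrees.

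SAP 8.2.2, the general efficacy section, gives the tabulation: "Duration of response will be summarized with number of responders, number and percentage of event/censorship, mean, standard deviation, minimum, maximum and median of duration", in months. No condition is attached, and nothing is said about how censored durations enter the mean or SD. Kaplan-Meier appears earlier in the same section, in optional wording that names PFS, although its list of timepoints includes DoR. The section also assigns Brookmeyer-Crowley confidence intervals to medians and quartiles.

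SAP 8.2.2.6, the DoR section, says: "The censoring rules for DoR are as described for PFS in Section 8.2.2.1", apart from exceptions for inadequate baseline and post-baseline assessments. The duration runs from first response to the "date of event or censoring". The estimator is conditional: "If at least 3 participants achieve an objective response and subsequently have an event, DoR will be estimated using the same Kaplan-Meier method". If that condition fails: "Otherwise, only listings will be provided".

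SAP 8.1.4 gives the general rule for time-to-event data: "The median, percentiles, and probabilities at particular points in time are estimated using the method of Kaplan and Meier".

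**The concern.** A mean of right-censored durations averages completed responses with responses that were merely cut off by the end of observation. The cut-off ones are entered as shorter than they are, so the result understates how long responses last, and the understatement grows as follow-up shortens. Here such a figure would stand in a table for a primary endpoint, beside a Kaplan-Meier estimate of the same quantity, with nothing to tell the reader that the two differ in kind.

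The second problem is one of instruction. For a cohort with fewer than 3 responders having an event, 8.2.2 requires a tabulated summary and 8.2.2.6 permits only listings. A programmer cannot follow both.

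**Working it through.** **The plan's own figure.** The only DoR result in the documents is in Protocol 1.2.3.2: median 11.6 months (95% CI 7.2, NE) at the 22 June 2022 cutoff. It cannot be reproduced without patient-level durations. The non-estimable upper limit fits a method that respects censoring.

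**What each rule covers.**

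| Statistic in 8.2.2 | Censoring handled elsewhere in the SAP? |
|---|---|
| Median | Yes: 8.1.4, the Brookmeyer-Crowley sentence in 8.2.2, and 8.2.2.6 |
| Mean, SD | No |
| Minimum, maximum | No; censored values are not marked |

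**Direction of the bias.** Let T be the true duration and C the time from response to censoring. The recorded value is X = min(T, C). X never exceeds T, so the mean of X cannot exceed the mean of T, and it is lower whenever a censored response would have continued. Averaging only the durations that ended in an event would not help, because under independent censoring shorter durations are more likely to be seen to end.

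**Size.** Inputs and assumptions:
- DoR is exponential with median 11.6 months (value from Protocol 1.2.3.2; the distribution is assumed). Rate λ = ln 2 / 11.6 = 0.05975 per month; true mean 1/λ = 16.74 months.
- C is independent of T and uniform on (a, b) (assumed). The first range, 0.3-24.4 months, borrows the follow-up range in Protocol 1.2.3.2, which is for all 41 patients and is not measured from response. The others show how the answer moves as follow-up lengthens.

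Formulas:
- Censored proportion p = [exp(-λa) - exp(-λb)] / [λ(b - a)]
- Mean of X = (1 - p)/λ

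For (0.3, 24.4): p = (0.9822 - 0.2327)/1.4401 = 0.520, and the mean is 16.74 × 0.480 = 8.0 months.

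| Censoring range (months) | Censored | Plain mean (months) | Below 16.74 by |
|---|---|---|---|
| 0.3-24.4 | 52% | 8.0 | 52% |
| 6-18 | 50% | 8.4 | 50% |
| 6-30 | 37% | 10.5 | 37% |
| 24-30 | 20% | 13.4 | 20% |

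Under this model the plain mean is low by exactly the censored proportion. Simulation with 26 responders (4,000 runs per range; 26/41 = 63.4%, the reported response rate) gave the same means, with Kaplan-Meier medians of 11.6, 11.6, 11.5 and 11.0 months in the same order.

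**How often the three-event conflict arises.** In the same simulations with 12 responders, the number in the Part 2A planning example (Protocol 9.3), fewer than 3 events occurred in 2.6% of runs with censoring at 0.3-24.4 months and 14.6% with censoring at 3-12 months. With 26 responders the figure was at most 0.2%. The conflict therefore matters mainly in small cohorts or early cuts. Such cohorts exist: SAP 8.2.2 summarizes efficacy by dose cohort, and Protocol 3.4 reports 3 responders each at 215 and 360 µg/kg. On those counts all three must have an event before 8.2.2.6 permits Kaplan-Meier.

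**The case against.** The strongest reply is that the DoR section, not the general one, governs. It specifies Kaplan-Meier, with rates at fixed times and confidence intervals, and nothing suggests that a plain mean would be the headline. Efficacy summaries involve no hypothesis test (SAP 8.2.2), no comparison between dose groups is planned (SAP 6.5), and Part 2 was sized on response rate (Protocol 9.3). All of that stands. It limits the consequence but does not supply a censoring rule for the mean and SD, which 8.2.2 still requires.

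A reader might go further and infer that the SAP produces two different medians, one of them a plain sample median. The documents do not support that. SAP 8.1.4, the Brookmeyer-Crowley sentence and 8.2.2.6 together make the median Kaplan-Meier on a natural reading. The list in 8.2.2 does resemble the SAP's template for ordinary continuous data, and that is a reason to state the method. A plain median, if used, would also not always be low: in the 26-responder simulations it averaged 6.7 months with censoring at 0.3-24.4 months, but 11.9 with censoring at 24-30 months, against a true 11.6.

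A reader might also infer that with fewer than 3 events an uncorrected table is all that would be reported. But 8.2.2.6 says "Otherwise, only listings will be provided" in that case. The defect is a contradiction between two sections, and nothing in the SAP makes the general one prevail.

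The size of the bias depends on assumed exponential durations and uniform censoring. The direction does not.

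**Conclusion.** The point holds for the mean and SD, and for the conflict between 8.2.2 and 8.2.2.6. As written, the mean of a primary endpoint mixes event and censoring times and understates duration whenever ongoing responses are censored. In the illustrated scenarios it is 20% to 52% low (8.0 to 13.4 months against 16.7), given exponential DoR with median 11.6 months and independent uniform censoring.

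It does not extend to the median or to the main DoR estimate. The documents do not show that the Kaplan-Meier analysis in 8.2.2.6 is biased or displaced. Because the analysis is descriptive and affects no test or sample size, the practical effect is modest. The correction is still worth making, since the alternative is a misleading number in a primary-endpoint table.

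**What to change.** Revise the DoR sentence in SAP 8.2.2 so that it:

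1. drops the mean and SD, or replaces them with a restricted mean at a stated horizon;
2. states that the median and quartiles are Kaplan-Meier estimates with Brookmeyer-Crowley confidence intervals;
3. marks censored values in the minimum and maximum;
4. keeps the counts of responders, events and censored responses;
5. makes the summary subject to the three-event rule in 8.2.2.6, with listings only below it.

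The cost is one SAP sentence and the matching table shell. No data collection, sample size or test changes.

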8.2.2.1. Progression-Free Survival (PFS)

PFS is the time from date of first dose to date of first documentation of PD in a progression or death due to any cause. PD or death after no more than 1 missing tumor assessment or date of first dose will be counted as an event according to the disease assessment date or date of death, as appropriate. The definitions of relapse, clinical relapse and relapse from CR are not to be used in calculation of progression free survival. Subjects will be considered to have progressive disease if they meet the criteria for progression even by a variable that was not considered as a measurable marker at baseline; however, for subjects who had a measurable serum or urine M-spike at baseline, progression cannot be defined by increases in serum FLC alone. In the IMWG criteria, clinical relapse subjects must also meet the criteria for progressive disease shown here to be classified as progressive disease for the purposes of calculating time to progression and progression-free survival.

Clinical relapse will be equivalent to PD. Note that a progression is defined as:

- 2 consecutive assessments of PD,
- or 1 PD as last efficacy assessment followed by permanent treatment discontinuation,

- or 1 PD following treatment discontinuation (EOT for both treatments in combined therapy - Part 1C and Part 1D). If the discontinuation is after PD but before the next response, then it is considered PD. If there are better responses before discontinuation, it is not considered PD to allow for possible pseudo progression from the treatment which is clinically possible and accepted.

The mITT analysis set will be used.

Censoring: Subjects without an event or with an event after 2 or more missed tumor assessments will be censored as described in Table 4. In addition, if a new anti-cancer therapy is started prior to an event, the subject will be censored on the date of the last adequate tumor assessment that documented no progression prior to the start of the new anti-cancer therapy.

An adequate post-baseline assessment is defined as an assessment where a response of sCR, CR, VGPR, PR, MR, SD, Relapse or PD can be determined based on IMWG response criteria for multiple myeloma. Subjects with no baseline disease assessment (including subjects with an inadequate baseline assessment) or with no adequate post-baseline disease assessments within 46 days for cohorts with 21 day cycles and 60 days for cohorts with 28 day cycles after the date of first dose will be censored on the date of first dose, unless the subject dies within 46 days for cohorts with 21 day cycles and 60 days for cohorts with 28 day cycles of the date of the first dose, in which case, death will be an event on date of death. Subjects will be considered to have progressive disease if they meet the criteria for progression by a variable that was not considered measurable at baseline.

Events and censoring rules are summarized in Table 4.

Table 4. Progression Free Survival

Situation	Date of Progression/Censoring¹	Outcome
Inadequate baseline assessment	First dosing date in Cycle 1 (or Cycle 0 for priming cohorts)	Censored
No on-study assessments	First dosing date in Cycle 1 (or Cycle 0 for priming cohorts)	Censored
Alive, on treatment ² and no Progression	Date of last objective tumor assessment ³	Censored
New anti-cancer therapy	Date of last adequate disease assessment that documented no progression prior to new anti-cancer therapy	Censored
Progression Documented on or between scheduled tumor assessments prior to treatment discontinuation ²	Date of first objective tumor assessment showing objective progression	Progressed (Event)
Withdrawal of consent prior and refusal to follow-up	Date of last objective tumor assessment prior to	Censored

	discontinuation ²	
Treatment discontinuation for undocumented progression, toxicity or other reason	Date of last objective tumor assessment prior to discontinuation ²	Censored
Death prior to first planned tumor assessment	Date of death	Death (Event)
Death without objective progression prior to treatment discontinuation ²	Date of death	Death (Event)
Death or progression after 2 or more missed tumor assessments ⁴	Date of last objective tumor assessment prior to the event	Censored
Lost to follow-up	Date of last objective tumor assessment ³	Censored

1. For date of censorship, if a tumor assessment takes place over a number of days (e.g., superficial lesions one day, scans another), the last date is used as the assessment date.
2. or within 28 days of discontinuation of treatment.
3. Date of last adequate disease assessment that documented no progression
4. This would be 46 days for cohorts with 21 day cycles and 60 days for cohorts with 28 day cycles

Reasons for censoring should be summarized according to the categories in Table 5.

Table 5. PFS Censoring Reasons and Hierarchy

Hierarchy	Condition	Censoring Reason
1	No adequate baseline assessment	No adequate baseline assessment
2	Start of new anti-cancer therapy before event.	Start of new anti-cancer therapy
3	Event after 2 or more missed tumor assessments/start date	Event after missing assessments ^a
4	No event and [withdrawal of consent date \geq date of first dose OR End of study (EOS) = Subject refused further FU]	Withdrawal of consent
5	No event and lost to follow-up in any disposition page	Lost to follow-up
6	No event and [EOS present OR disposition page for any EPOCH after screening says subject will not continue into any subsequent phase of the study] and no adequate post-baseline disease assessment	No adequate post-baseline disease assessment
7	No event and none of the conditions in the prior hierarchy are met	Ongoing without an event

^a 2 or more missed tumor assessment.

Disease Assessment Date: The Date of Disease Assessment at each nominal timepoint as provided by the investigator on the IMWG response CRF page will be utilized for the respective analyses.

Adequate Baseline Disease Assessment: Adequate baseline is defined using the following criteria:

- All baseline disease assessments (IMWG responses) must be within 28 days prior to and including the date of first dose;
- Measurable disease based on IMWG criteria as defined by at least 1 of the following:
 - Serum M-protein ≥ 0.5 g/dL by SPEP;
 - Urinary M-protein excretion ≥ 200 mg/24 hours by UPEP;
 - Serum immunoglobulin FLC > 10 mg/dL (> 100 mg/L) AND abnormal serum immunoglobulin kappa to lambda FLC ratio (< 0.26 or > 1.65).

Adequate Post-baseline Disease Assessment: An adequate disease assessment is defined as an assessment where a time-point response of sCR, CR, VGPR, PR, minimal response (MR), Stable Disease (SD) or PD has been provided.

Timepoints where the response is not evaluable or no assessment was performed will not be used for determining the censoring date for time-to-event endpoints including PFS, DOR and DOCR.

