- If patients were treated with daratumumab less than 114 days prior to planned treatment day, daratumumab will interfere with SPEP, UPEP, SIFE and UIFE assays. Therefore, for these patients, FLC assay should be completed at screening, C1D1, and all subsequent disease assessments. In these patients who previously received daratumumab serum and urine M-spike if measurable at baseline in these patients should also be followed at the same timepoints as FLC with the most representative marker of disease status used for determination IMWG assessment.
- Beta-2 microglobulin. This will be collected on the first day of treatment.

All samples will be collected prior to investigational product administration on days whereby investigational product is to be administered. In patients with two M-protein bands at the start of therapy, unless the second band is due to daratumumab or other therapeutic mAb interference, the sum of the two spikes should be used for monitoring of disease. When a complete response (CR), or a clinical or biochemical progression is suspected, SPEP, serum SIFE, UPEP, UIFE and FLC tests will be repeated within 1 to 4 weeks.

Note that if a patient had measurable serum or urine M-spike at baseline, unless the band is due to daratumumab or measurement of M-spike is confounded by the presence of daratumumab or other therapeutic mAb, progression cannot be defined by increases in serum FLC alone. Serum FLC levels should only be used for response assessment when both the serum and urine M-component levels are deemed not measurable or uninterpretable. Furthermore, careful attention should be given to new positive immunofixation results appearing in patients who have achieved a CR, when the isotype is different. This may represent oligoclonal immune reconstitution and should not be confused with relapse; these bands typically disappear over time.

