Appendix 2. THE INTERNATIONAL MYELOMA WORKING GROUP (IMWG) RESPONSE CRITERIA FOR MULTIPLE MYELOMA

All response categories require two consecutive assessments made any time before starting any new therapy. Patients must have measurable disease at enrollment (study entry).

Measurable disease is defined as:

- Serum M-protein ≥ 0.5 g/dL (5 g/L); (See [inclusion criteria](#) for modifications);
- Urine M-protein ≥ 200 mg/24 h;
- Serum FLC assay: involved FLC level ≥ 10 mg/dL provided serum FLC ratio is abnormal.

Whenever more than one parameter is used to assess response, the overall assigned level of response is determined by the lower or lowest level of response. Patients will continue in the last confirmed response category until there is confirmation of progression or improvement to a higher response status; patients cannot move to a lower response category.

| Response | IMWG Criteria |
|-----------------------------------|--|
| Stringent Complete Response (sCR) | 
 • Complete response as defined below plus normal free light chain (FLC) ratio and absence of clonal cells in bone marrow biopsy by immunohistochemistry (κ/λ ratio $\leq 4:1$ or $\geq 1:2$ for κ and λ patients, respectively, after counting ≥ 100 plasma cells).² • In patients whereby the only measurable disease is by serum FLC levels, sCR is defined as normal FLC ratio of 0.26 to 1.65 plus absence of clonal cells in bone marrow as defined above. |
| Complete Response (CR) | 
 • Negative immunofixation on the serum and urine and disappearance of any soft tissue plasmacytomas and $<5\%$ plasma cells in bone marrow aspirates.¹ • In patients whereby the only measurable disease is by serum FLC levels, CR is defined as normal FLC ratio of 0.26 to 1.65 plus criteria listed above. |
| Very Good Partial Response (VGPR) | 
 • Serum and urine M-protein detectable by immunofixation but not on electrophoresis. or • $\geq 90\%$ reduction in serum M-protein plus urine M-protein level <100 mg/24 hr. • In patients whereby the only measurable disease is by serum FLC levels, VGPR is defined as a $>90\%$ decrease in the difference between involved (tumor) and unininvolved (non-tumor) serum FLC levels. |

PF-06863135

C1071001

Final Protocol Amendment 9, 28 March 2023

| Response | IMWG Criteria |
|---------------------------------------|---|

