| Partial Response (PR) | 
 • $\geq 50\%$ reduction of serum M-protein and reduction in 24 hours urinary M-protein by $\geq 90\%$ or to $< 200 \text{ mg/24 hr}$. • If the serum and urine M-protein are unmeasurable,⁴ a $\geq 50\%$ decrease in the difference between involved and uninvolved FLC levels is required in place of the M-protein criteria. • In patients whereby the only measurable disease is by serum FLC levels, PR is defined as 50% reduction in difference between involved and uninvolved FLC. • In addition to these criteria, if present at baseline, a $\geq 50\%$ reduction in the size (SPD)² of soft tissue plasmacytomas is also required. |
| Minimal Response (MR) | $\geq 25\%$ but $\leq 49\%$ reduction of serum M-protein and reduction in 24-h urine M-protein by 50–89%. In addition to the above listed criteria, if present at baseline, a 50% reduction in the size (sum of the products of the maximal perpendicular diameters of measured lesions [SPD]) ³ of soft tissue plasmacytomas is also required. |
| No Change/Stable Disease (SD) | Not meeting criteria for CR, VGPR, PR, MR or progressive disease. |
| Progressive Disease (PD) ⁵ | 
Any one or more of the following criteria:
 
 • Increase of $\geq 25\%$ from lowest response value in any one or more of the following: • Serum M-component and/or (the absolute increase must be $\geq 0.5 \text{ g/dL}$);⁴ • Serum M-protein increase $\geq 1 \text{ g/dL}$, if the lowest M component was $\geq 5 \text{ g/dL}$; • Urine M-component and/or (the absolute increase must be $\geq 200 \text{ mg/24 hr}$). • In patients without measurable serum and urine M-protein levels, the difference between involved and uninvolved FLC levels (absolute increase must be $> 10 \text{ mg/dL}$); • Appearance of a new lesion(s), $\geq 50\%$ increase from nadir in SPD¹ of > 1 lesion, or $\geq 50\%$ increase in the longest diameter of a previous lesion $> 1 \text{ cm}$ in short axis. |
| Clinical Relapse | Clinical relapse requires one or more of the following criteria: |

PF-06863135

C1071001

Final Protocol Amendment 9, 28 March 2023

| Response | IMWG Criteria |
|----------|---|

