4. All relapse categories require two consecutive assessments made at any time before classification as relapse or disease progression and/or the institution of any new therapy. To confirm response or progressive disease, two discrete samples are required and testing cannot be based upon the splitting of a single sample. In the IMWG criteria, CR patients must also meet the criteria for progressive disease shown here to be classified as progressive disease for the purposes of calculating time to progression and progression-free survival. The definitions of relapse, clinical relapse and relapse from CR are not to be used in calculation of time to progression or progression free survival. Patients will be considered to have progressive disease if they meet the criteria for progression by a variable that was not considered measurable at baseline; however, for patients who had a measurable serum or urine M-spike at baseline, progression cannot be defined by increases in serum FLC alone.
5. For progressive disease, serum M-component increases of ≥ 1 mg/dL are sufficient to define relapse if starting M-component is ≥ 5 g/dL.

PF-06863135

C1071001

Final Protocol Amendment 9, 28 March 2023

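### Protocol 7.2.1 lets a light-chain rise alone define progression when a therapeutic antibody confounds the M-spike; both Appendices 2 and SAP 8.2.2.1 bar it with no exception

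*SAP*

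**What the plan says.** Protocol 7.2.1 bars progression by serum FLC alone in a patient with a measurable baseline M-spike, "unless the band is due to daratumumab or measurement of M-spike is confounded by the presence of daratumumab or other therapeutic mAb". For patients who had daratumumab less than 114 days before treatment, it asks for FLC and any measurable M-spike to be followed together, "with the most representative marker of disease status used for determination IMWG assessment". On response it says: "Serum FLC levels should only be used for response assessment when both the serum and urine M-component levels are deemed not measurable or uninterpretable".

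Protocol Appendix 2, footnote 4, states the bar without the exception: "for patients who had a measurable serum or urine M-spike at baseline, progression cannot be defined by increases in serum FLC alone". SAP Appendix 2, footnote 4, and SAP 8.2.2.1 repeat it for subjects: "for subjects who had a measurable serum or urine M-spike at baseline, progression cannot be defined by increases in serum FLC alone". Further on, after the definition of an adequate post-baseline assessment, SAP 8.2.2.1 again says that a subject may progress "by a variable that was not considered measurable at baseline", this time with no FLC limit.

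For partial response, the Appendix 2 tables of both documents let FLC take the place of M-protein under the condition "If the serum and urine M-protein are unmeasurable". They do not mention M-protein that can be measured but not interpreted.

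**The concern.** Four places define the same event, and one of them has an exception that the other three lack. The omission is not simple silence, because the three restate the general rule in full and leave out only the qualification.

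The exception exists for patients whose M-spike cannot be trusted because a previous antibody shows up in the assay. Their light chains may be the only readable laboratory marker. Whether a light-chain rise ends their response depends on which page the investigator or programmer has open. Duration of response is a Part 2 primary endpoint together with ORR, and PFS and the other duration endpoints rest on the same definition of progression.

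**Working it through.** The documents give no figure to reproduce here, so the check sets the texts side by side.

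| Place | FLC-only progression with a measurable baseline M-spike | Antibody exception |
|---|---|---|
| Protocol 7.2.1 | Barred | Yes: daratumumab band, or confounding by daratumumab or another therapeutic antibody |
| Protocol Appendix 2, footnote 4 | Barred | None |
| SAP 8.2.2.1, first paragraph | Barred | None |
| SAP Appendix 2, footnote 4 | Barred | None |
| SAP 8.2.2.1, later sentence | Not mentioned; any variable unmeasurable at baseline counts | Not applicable |

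**One patient, step by step.** Take a patient with a measurable baseline serum M-spike that is confounded by daratumumab. Later, the difference between involved and uninvolved FLC rises by at least 25% from its lowest value and by more than 10 mg/dL, on two consecutive assessments. No M-protein criterion is met and there is no new lesion.

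1. Under Protocol 7.2.1 the exception applies, so this is progression.
2. Under footnote 4 of either Appendix 2 it is not. The progressive-disease row points the same way, since its FLC criterion is written for patients without measurable serum and urine M-protein.
3. Under the first paragraph of SAP 8.2.2.1 it is not.
4. Under the later sentence of SAP 8.2.2.1 it is progression if FLC was not measurable at baseline. That would hold for any patient, confounded or not.

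**Effect on the endpoints.** If the rise counts, PFS and duration of response end on that date, as do the durations of complete response (SAP 8.2.2.7) and stable disease (SAP 8.2.2.10) where they apply. If it does not count, the patient stays at risk until another criterion is met or the patient dies. Alternatively the patient is censored: SAP Table 4 censors both discontinuation for undocumented progression and the start of new anti-cancer therapy. The event is then delayed or turned into a censoring. The documents do not show how often each would happen.

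**Who could be affected.** Inclusion criterion 2 calls for previous anti-CD38 therapy where approved and available. Exclusion criterion 11 sets a 30-day floor after antibody therapy, alongside a five-half-life condition. Section 7.2.1 expects daratumumab interference below 114 days. For daratumumab, the 30-day floor leaves a window of 114 − 30 = 84 days. The progression exception itself has no day limit and also covers other therapeutic antibodies. Within this group, a patient must also have a baseline M-spike that is both measurable and confounded. Neither document counts such patients.

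**The case against.** **Precedence.** SAP Section 2 says the SAP supersedes the protocol's statistical considerations, so the bar might simply govern. However, the same section promises to identify substantial differences, and this one is not identified. Protocol Section 9 says major changes to primary endpoint definitions will also appear in a protocol amendment. Protocol Appendix 2 contradicts Protocol 7.2.1 in any case, and SAP precedence cannot resolve that.

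**Investigator reporting.** SAP 6.1 takes responses as the investigator reports them, and the SAP describes no step that re-derives progression from laboratory values. This stands in part: an investigator who follows 7.2.1 would probably have the event counted. But another investigator may follow Appendix 2 of the same protocol, and identical data could then be coded differently.

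**Confounded means unmeasurable.** If so, the FLC criterion would already apply. No text says this. Section 7.2.1 treats these patients as having a measurable spike and then exempts them, and inclusion criterion 1c lists unmeasurable and uninterpretable M-protein as separate cases.

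**Interference fades.** An 84-day window is short beside the median duration of response of 11.6 months in Protocol 1.2.3.2, so many progressions may come when the M-spike is readable again. That is fair and limits the numbers. It does not remove the conflict, because the bar depends on the baseline M-spike and does not lapse when the interference does.

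**Limited consequence.** SAP 8.2.2 plans no formal efficacy testing, enrolment is complete, and Protocol 1.2.3.1 lists 15 patients in Part 2A and none in the other expansion cohorts. All of this stands. The matter concerns how an event is defined and reported; no test or decision rule depends on it.

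**Conclusion.** The contradiction on progression is real and can be read directly from the text. It affects PFS, duration of complete response, duration of stable disease and the end of duration of response, in patients whose baseline M-spike is confounded by a therapeutic antibody. That subgroup could be small, and no numerical effect can be stated.

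A reader might infer more, in three ways that the documents do not support.

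- **That ORR is understated because an antibody band holds response below partial response.** The rule that "the overall assigned level of response is determined by the lower or lowest level of response" applies only when more than one parameter is used, and 7.2.1 directs assessment to the most representative marker. SAP 8.2.2.1 contains no lowest-level rule. Section 7.2.1 also leaves a second band due to the antibody out of the monitored sum, and a fading band would lower measured M-protein. The quoted bar concerns progression only.
- **That median duration of response shifts by a calculable amount.** This needs the affected share and the proportion of their progressions shown by FLC alone, and neither is given. It would also treat delayed events as lost. The 11.6 months comes from responders among 41 patients pooled across two schedules, not from Part 2 alone.
- **That the progression exception is confined to the 114-day window.** That limit belongs to the FLC monitoring instruction and does not appear in the exception.

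**What to change.** 1. In Protocol Appendix 2 footnote 4, SAP 8.2.2.1 and SAP Appendix 2 footnote 4, add after the bar: *unless the band is due to, or its measurement confounded by, daratumumab or another therapeutic mAb*. Cross-refer to it from the FLC line of the progressive-disease row.
2. In SAP 8.2.2.1, delete the later any-variable sentence, or give it the same FLC limit and the same exception as the first paragraph.
3. As a minor alignment, let FLC replace M-protein in the partial-response row of both Appendix 2 tables when M-protein is *unmeasurable or uninterpretable*, as 7.2.1 already allows.

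There is no need for a rule that fixes the marker at baseline. Section 7.2.1 has none, and it would be a new response criterion.

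The cost is a few lines in each document, with the SAP change made before database lock. No new data are needed: 7.2.1 already requires FLC at screening, at Cycle 1 Day 1 and at every later disease assessment for patients with recent daratumumab, and treatment history is collected at screening. A listing of patients whose progression rests on the exception would show the size of the issue, but is optional.
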